10.1 General remarks

The primary endpoint is feasibility. The secondary endpoints are duration of relief from local symptoms, i.e. local symptom progression free survival (LPFS), overall survival, treatment toxicity (RTOG/CTCAE 4.0), Quality of life (EORTC-QLQ-C30 and EPIC26), and change in ADC as surrogate marker of response (21-25). Patients are scheduled for protocol specific follow-up visits at 1, 3, 6 months after end of radiotherapy. Additional MRI (T2w and DWI) will be performed at 1 and 6 months after end of radiotherapy or in case of progression of the dominant symptom.

Preferred technique is hypo-fractionated with high precision radiotherapy (radiosurgery or stereotactic radiotherapy) with few (1 to 5) fractions and ablative total dose. Daily IGRT is mandatory for hypo-fractionated regimens. For the treatment of thoracic lesions and metastases in the upper abdomen, techniques for motion compensation (e.g. breath-hold- or gating techniques) should be used, if available. In specific situations (e.g. spinal metastases with involvement of the spinal canal or cord compression or metastases with infiltration of hollow organs), however, lower doses of radiotherapy may be necessary for adherence of dose constraints or to avoid radiation-induced complications such as perforation. In these cases, moderately hypo-fractionated or even conventionally fractionated regimens should be used. The total dose should exceed at least a dose equivalent to 50Gy in conventional fractionation.

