The aim of the present study will be to conduct a feasibility study of a new short palliative radiotherapy regime that apply to patients with metastatic HRPC patients presenting with a dominating debilitating symptom and an expected reasonable survival. The dominant symptom can be such as pain, urinary retention, chronic rectal obstruction, bleeding etc., caused by localized progression of the patient's metastatic prostate cancer. This new approach will apply magnetic resonance imaging (MRI) to verify correspondence between the progressing HRPC lesion (DSL =the dominant symptomatic lesion) and the patients corresponding dominant symptom. Diffusion weighted MR imaging (DWI) will apply to identify both the lesion and the most aggressive part of the lesion. The symptomatic lesions will be treated using precision radiotherapy (IGRT+IMRT/VMAT or SBRT/SRS if available) with a dose of 4 x 5 Gy, while for the most aggressive part of the lesion the dose will be escalated to 4 x 7 Gy using a simultaneous integrated boost (SIB) technique.

4 Objective

This prospective study will evaluate the feasibility as the primary endpoint. Secondary endpoints are visual analog score (VAS) of the dominating symptom, symptom progression free survival, evaluation of radiation induced acute toxicity, the influence on quality of life, the progression free survival and change in volume and ADC statistics from baseline as surrogate marker of local response to radiotherapy. The study will analyze patient characteristics, relevant comorbidities and tumor related factors correlation to outcomes. Based on the results of this study, a prospective randomized phase II/III dose escalation study may suggested.

5 Study design and participating centers

This is an international, multi-center single arm prospective feasibility study. Participating sites are:

1. University Hospital Sjaelland, Naestved, Department of Oncology
2. UKSH Campus Kiel, Department of Radiation Oncology
3. UKSH Campus Luebeck, Department of Radiation Oncology

6 Inclusion and exclusion criteria

Patients can be included in the study if they fulfill all of the following inclusion criteria and none of the following exclusion criteria.

Inclusion criteria:

- Patients with hormone refractory biopsy proven prostate cancer (HRPC)
- Presenting with a dominating debilitating symptom
- Expected median survival of 3-12 months (6)
- Focal irradiation of lesion is feasible
- Systemic therapy according to guidelines

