10.3 Target volumes

Patients included in the study will be subjected to a protocol-specific MRI examination (see MR sequence and example of target delineation in appendix 19-20). A radiologist will read the MRI scan to validate correspondence between MR lesion and the patients dominating symptoms. In case of more than one lesion, decision on priority of target volumes will be made by the radiation oncologist based on clinical expertise. An ADC map will be calculated for the lesion using the DWI sequences. A cutoff ADC value of less than 1200×10^{-6} mm²/s in combination with a T2w image will be used to predict the MR lesion (GTV1) (26). The most aggressive part of the lesion (GTV2) will be defined using ADC of less than or equal to a cutoff value calculated as the median ADC value for the GTV1 (25). Notice that GTV2 need not to be one coherent volume, but may consist of several sub-volumes.

For the definition of target volumes, the following aspects should be considered: The clinical target volume (CTV) is the visible macroscopic tumor (GTV). The safety margin for the planning target volume (PTV) should be according to the department standard, and depending on the radiation technique used. The margin for the PTV2 for CTV2 may be chosen to be smaller than for PTV1 as this volume is enclosed in the CTV1, which receives a dose of 4 x 5Gy already.. For the treatment of breathing-dependent lesions (upper abdomen), treatment techniques with motion compensation (e.g. breath-hold or gating) should be used. All four fractions of the treatment should be given within two weeks of starting the radiotherapy.

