10.6 Start of radiotherapy

Radiotherapy should be started within three weeks after inclusion of the patient in the study.

11 Trial Procedures and Assessment

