11.4 Follow-up visits

Protocol visits are required at registration for the trial and at end of radiotherapy and at 1,3 and 6 months after end of treatment (see flowchart in appendix 3). At this time, the following examination will be performed:

- Review of concomitant medication, analgesia, opioids, current systemic anti-cancer treatment
- Review of clinical routine blood and radiology results
- Dominant symptom score (VAS)
- Acute toxicities of radiotherapy , RTOG/NCI score
- Quality of life (EORTC-QLQ C30) (only at 6 months)
- ECOG performance status
- Assessment of AE/SAE

All later visits are scheduled according to standard guidelines and institutional procedures.

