16.3 Analysis

Patient and tumor characteristics are given as absolute and relative frequencies. Doses, volumes, fractions are listed by technique, by localization of metastasis, and by size. Maximum and median doses applied to organs at risk are described as median, inter-quartile range, and maximum. Summary compliance measures use the worst observation. Further parameter estimation, confidence intervals and tests using data at the metastasis level account for correlation by using GEE methods.

Toxicities are tabulated by grade and time and shown as time profiles of cumulated grades. Adverse events are listed by system organ class (MedDRA), intensity and causality. Progression free survival is estimated using the Kaplan-Meier method.

17 Early termination

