17.2 Study termination in individual patients

Participation in the study and study specific therapy must be stopped at any time during the study in individual patients for any of the following reasons

- withdrawal of informed consent by the patient
- severe toxicity with limitations or unacceptable risks to administer further study therapy
- inter current disease with limitations to administer protocol therapy
- progression of disease

[figure not shown]
18 Ethical and legal aspects

The study will be conducted according to the declaration of Helsinki. Approval by the ethical committees of the participating institution is required prior to initiation of the study. Patients must be fully informed about the study and give informed consent prior to inclusion. National rules for data protection must be obeyed.

The study concept has been evaluated by the expert panel of DEGRO (German Association of Radiation Oncology). Approval by the German Radiation Protection Authority (BfS) is not required. A patient insurance will be taken out before the start of the trial for all patients, if necessary according to national rules. The trial will be registered in a primary study register before the start of the study.

This study receive financial support from EU via the Interreg project.

19 Appendix 1 – Calculation of median survival

20 Appendix 2 – Diagnostic MR Protocol sequences

MR protocols are modified/adapted from (24) and (27) to cover the lesion that explains the dominant symptom.

The MR sequence protocol must contain an anatomical (T2w) axial sequence (reference scan see table below), that can be co-registered to the planning CT, ie. the reference scan must include enough rigid anatomical structures for a co-registration with good accuracy. The remaining MR sequences must cover the dominant lesion with adequate margin (typically 50 mm) that will allow for outline of the lesion in 3D. All MR sequences must be acquired with the same dicom origo, ie neither, the patient nor, the dicom origo may be moved between sequence acquisitions. This will allow all MR images to be co-registered to the planning CT.

Sequence	Directions	Slice mm	TR msec	TE msec	Avg
T2-weighted fast SE	Ax* / Cor / Sag	3/ 5/ 5	2850	80	4
T1-weighted GRE SPIR**	Ax	5	1000	3.7	4
Proton density-weighted fast SE	Ax	5	2850	4.7	4
DW imaging*** with free-breathing SE EPI SPIR*	Ax	5	4687	64	8

Avg = number of sample averages

* Reference scan = T2w axial images

[figure not shown]

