** SPIR = Spectral Presaturation with Inversion Recovery

*** b0 images and three b-values: b=50, 500 og 900 sec²/mm

[figure not shown]
Fat suppression should be preferably be done with a selective method as SPIR if possible. If not the STIR method, less specific, alternative method to use. Some post processing of MR images may be necessary to suppress noise in the images before automatically outlining the GTV. The ADC map should be calculated using all three b-values and mono-exponential fitting.

21 Appendix 3 - Target outline procedure

[figure not shown]
The following example demonstrate the target outline procedure on the MR images. This example is a reconstruction based on images from (28)

The target is outlined on the T2W image. This image is co-registered to the ADC map and the outline is transferred to the ADC map.

The outline transferred to the ADC map is subsequently corrected using a threshold for the $ADC < 1200 \text{ mm}^2/\text{s}$ for the target. This target is named GTV1

The median ADC value for the GTV1 target. The median value is used as threshold to obtain the most aggressive part of the target. This subvolume is named GTV2.

22 Appendix 4 – Flowchart for the study

	Inclusion	Visit 1 Baseline before RT	After RT	Visit 2 1 month	Visit 3 3 month	Visit 4 6 month
Screening / Inclusion	X					
Informed Consent	X					
Medical history	X					
MR scanning		X		X		X
Anamnesis		X				
Medical examination		X	X	X	X	X
Local Symptoms		X	X	X	X	X
Quality of Life		X				X
Toxicity		X	X	X	X	X
LPFS			X	X	X	X
ADC Response			X			X
Survival			X	X	X	X
AE/SAE			X	X	X	X
Concomitant medication		X	X	X	X	X
VAS		X	X	X	X	X
ECOG		X	X	X	X	X

23 References:

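### Survival follow-up is scheduled only from end of radiotherapy and participation ends with therapy, so men who never start or who stop early can drop out of the survival data

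*Protocol*

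**What the plan says.** Section 10.1: "Patients are scheduled for protocol specific follow-up visits at 1, 3, 6 months after end of radiotherapy". Section 11.4 adds the earlier contacts: "Protocol visits are required at registration for the trial and at end of radiotherapy and at 1,3 and 6 months after end of treatment".

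In the Appendix 4 flowchart the survival row reads "Survival X X X X". Its four marks fall under the after-radiotherapy column and the 1-, 3- and 6-month visits. The LPFS and AE/SAE rows have the same pattern. VAS, toxicity, ECOG and concomitant medication are also marked at the baseline visit.

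Two timing rules bound the interval before follow-up begins. Section 10.6: "Radiotherapy should be started within three weeks after inclusion of the patient in the study". Section 10.3: "All four fractions of the treatment should be given within two weeks of starting the radiotherapy". Section 10.1 also allows longer schedules in specific situations.

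Section 17.2: "Participation in the study and study specific therapy must be stopped at any time during the study in individual patients for any of the following". The grounds it then lists are withdrawal of consent, severe toxicity, intercurrent disease and disease progression.

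On analysis, section 16.3 says only: "Progression free survival is estimated using the Kaplan-Meier method". It gives no time origin and no analysis set.

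**The concern.** Survival and progression are secondary endpoints in men selected for an expected median survival of 3 to 12 months. In such a group, failing to start or finish a short course is plausibly a sign of poor prognosis. The protocol creates two routes by which these men can leave the data.

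- **Never irradiated.** The protocol MRI is done in patients already included (section 10.3). Symptoms that do not match the MRI, and dose constraints that cannot be met, are exclusion criteria (section 6). A man can therefore be included and then go no further. He has no end-of-radiotherapy date, so nothing in the calendar applies to him.
- **Stopped early.** He has a last-fraction date, but section 17.2 ends his participation along with his therapy. Because the rule applies at any time and lists progression, read literally it also ends survival follow-up at progression after a completed course. That sits badly with section 11.5, which asks for an MRI at progression of the dominant symptom. The two passages need to be reconciled as to follow-up.

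A later analysis plan can choose a time origin, but it cannot recover survival status that was never collected. Section 4 says the results may lead to a randomised phase II/III study, so an optimistic survival figure could be carried into its design.

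**Working it through.** **Inputs from the protocol.** Inclusion to start, up to 3 weeks (10.6). Course length, up to 2 weeks (10.3). Expected median survival, 3 to 12 months (section 6). Drop-out 30%, 24 evaluable and 34 included (16.1).

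**The plan's own figure.** 24 / (1 − 0.30) = 34.3, stated as 34. The plan thus expects to lose about 34 − 24 = 10 men. Section 16.1 defines these losses as exclusion or withdrawn consent, not as death or non-completion.

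**Assumptions added here.** Exponential survival, and the longest window for the four-fraction course: 3 + 2 = 5 weeks = 1.15 months.

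**Step 1: deaths before end of radiotherapy.** P = 1 − 0.5^(1.15/m) for median m.

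| Median m (months) | Death within 5 weeks | Of 34 |
|---|---|---|
| 3 | 23.3% | 7.9 |
| 6 | 12.4% | 4.2 |
| 12 | 6.4% | 2.2 |

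**Step 2: clock from inclusion, but only men reaching end of radiotherapy recorded.** True 6-month survival is 0.5^(6/m). The recorded figure is 0.5^((6 − 1.15)/m).

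| Median m (months) | All included | Only those reaching end of radiotherapy | Difference (points) |
|---|---|---|---|
| 3 | 25.0% | 32.6% | 7.6 |
| 6 | 50.0% | 57.1% | 7.1 |
| 12 | 70.7% | 75.6% | 4.9 |

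Now let medians be uniform on 3 to 12 months and write S(t) for the average of 0.5^(t/m). S(6) = 54.4% and S(1.15) = 88.6%. The recorded figure is 54.4 / 88.6 = 61.4%, about 7 points too high.

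**Step 3: clock from end of radiotherapy, losses unrelated to prognosis.** S(7.15) / S(1.15) = 48.7 / 88.6 = 55.0%, against 54.4% from inclusion. The difference is under 1 point. With a single median it would be zero, because exponential survival has no memory.

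**Step 4: clock from end of radiotherapy, non-completion linked to prognosis.** By simulation, let the probability of non-completion among men alive at 5 weeks be logistic in minus log survival time, with slope s. Set total non-completion, including early deaths, to 20% or 30%. The slopes and the 20% are assumptions. The 30% borrows the drop-out figure, which section 16.1 defines differently.

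| Slope s | 20% non-completion | 30% non-completion |
|---|---|---|
| 0 | 55% | 55% |
| 1 | 58% | 62% |
| 2 | 60% | 67% |

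Against 54%, the overstatement is about 4 to 12 points for slopes 1 to 2. Median survival reads 7.7 to 9.3 months instead of 6.9.

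**The case against.** The strongest reply is that sections 10.1 and 11.4 fix visit dates, not an analysis. Several stronger readings are tempting, and the documents do not support them.

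- *Overall survival is defined from end of radiotherapy.* No section says so. Section 16.3 gives no origin, which may properly be left to an analysis plan that is not shown.
- *The secondary results describe completers only.* No analysis set is stated. Section 14 sends the adjudication committee the scans and plans of all patients.
- *Non-completers have no time zero and no visit.* Every included man is registered, and the registration and baseline visits come before radiotherapy. VAS is recorded at baseline. A man who stops early has a last-fraction date.
- *Deaths before the end of treatment go unrecorded.* Section 12.1 makes death an SAE, reportable within 24 hours of awareness and not tied to a visit.

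All of this stands, and it narrows the point to follow-up of men who never start or who leave. There the reply is weaker. Registration and baseline visits give no outcome. SAE reporting depends on someone becoming aware, and no contact is scheduled to ensure that once participation has ended.

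It is also fair that timing toxicity, symptom and ADC visits from end of treatment is sensible, that the 5-week window is the longest allowed for the four-fraction course, and that the primary endpoint is unaffected. Finally, analysing every included man brings in some whom the MRI later shows to be ineligible, and men who withdraw consent may not be traceable.

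**Conclusion.** The point holds as a gap in data collection. Visits and survival recording hang on end of radiotherapy, participation ends with therapy, and nothing provides for survival follow-up of a man who never starts. Applied as written, this risks losing men with poor prognosis and making survival and PFS look better than they are for the men recruited.

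The size is uncertain. Under exponential survival, medians of 3 to 12 months and a 5-week window, the overstatement in 6-month survival runs from under 1 point (Step 3) to about 7 points (Step 2). It is larger only if non-completion follows prognosis, which section 17.2's stopping reasons make plausible but which the protocol does not quantify. A reader might infer an established immortal-time bias of 4 to 12 points. That range rests on assumed slopes and should not be quoted as a property of the plan. No sample-size figure changes. The correction is worth making because it is cheap and the lost data cannot be recovered later.

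**What to change.** - **Section 11.4 and the flowchart:** record survival and SAEs from inclusion for every included patient who has not withdrawn consent to follow-up, including those never irradiated.
- **Section 17.2:** separate stopping study therapy from ending follow-up, so that toxicity, intercurrent disease or progression does not by itself end survival recording. This leaves the rules for stopping therapy untouched.
- **Section 16.3:** count OS and PFS from inclusion in all included patients, and show irradiated patients or completers as a sensitivity analysis. This also deals with men found ineligible after the MRI. If the analysis plan already sets this origin, only the collection changes are needed.
- Visits for toxicity, symptoms and ADC response may stay timed from the last fraction.

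The cost is protocol wording, a status check for a few patients and slightly less favourable survival figures. No extra patients or procedures are needed.

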Exclusion criteria (recruitment is not possible if any -at least one- criterion is met)	
 • Relevant comorbidity (with limitations to administer radiotherapy according to protocol) • Prior radiotherapy which results in limitations to administer radiotherapy according to protocol • No large metal implants in vicinity of lesion • Department dose constraints for normal tissue can't be met • Large bony lesions with extensive osseous destruction • Patients symptoms do not correlate with MR findings
Study therapy	
 • Image guided radiotherapy (IGRT) with hypo-fractionated simultaneous integrated boost (IMRT) • GTV1 = MR T2w lesion and ADC $\leq 1200 * 10^{-3}$ mm2/s • GTV2 = MR T2w lesion and ADC \leq median ADC in GTV1 • Each lesion is a CTV, CTV = GTV • PTV=CTV+ margin according to department standards • Dose-fractionation • CTV1: 4 x 5 Gy • CTV2: 4 x 7 Gy
Primary endpoint	Feasibility: Proportion of study participants that complete radiotherapy with $\geq 90\%$ of prescribed dose
Secondary endpoints	
 • Dominant symptom (VAS) • Progression-free survival >6 months • Overall survival

	
• Acute toxicity• Quality of life• Change in ADC from before to end of treatment• Change in ADC from before to 6 month post treatment
Sample size	34 patients has to be included in the study
Study sites	University Hospital Sjaelland, Naestved UKSH Campus Kiel UKSH Campus Luebeck
Time table	Recruitment period: 12 months Start of study: March 2018 End of study: March 2019 Follow-up: minimum \geq 6 months
Financing	Interreg (InnoCan)

3 Background and rationale

Prostate cancer is the major cause of cancer death in men living in developed countries. Large autopsy studies found that patients that presented prostate cancer demonstrated metastatic disease in 35% of cases. Prostate cancer metastases were 90% bone metastases, with 90% of the bone metastases involved the spinal cord, followed by lung (46%), liver (25%) and pleura (21%). Another important pathway is the lymphatic system, which is involved in 9 to 16% of cases, especially at the level of obturator, pre-sacral, internal, and common iliac arteries, and sometimes even the extra-regional para-aortic chains (1).

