10.4 Dose specification

The dose will be prescribed as 95%-PTV-coverage. The favorite technique is ablative radiosurgery or hypo-fractionated stereotactic radiotherapy if available, otherwise VMAT or IMRT is allowed. Recommended treatment regime

Technique	Dose and fractionation regimens
Hypo-fractionated regime	PTV1: 4F x 5Gy, total dose 20Gy PTV2: 4F x 7Gy, total dose 28Gy

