16.1 Case number

The objective of this study is to investigate the feasibility of applying hypo-fractionated radiotherapy to treat a dominant symptomatic lesion in patients with HRPC. The hypothesis is that at least 90% of the recruited patients complete combined systemic and local treatment with at least 90% of scheduled radiation dose administered. We use a two-sided one-sample proportion score test to compare the proportion of feasible cases to a reference value of 90%. We want to detect any difference with statistical significance of 5% and a power of 80% for not overlooking a true proportion non-feasible of 70%. The necessary sample size is estimated to 24 cases. Drop-out may happen either due to exclusion, or because patients withdraw their consent for participation. For patients with poor prognosis a realistic drop-out rate is estimated to be 30%, which implicated that **34 patients** must be included in the study to reach significance.

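### The primary endpoint does not tie the 90% dose criterion to 4 x 5 / 4 x 7 Gy, so an included patient who completes a Section 10.1 substitute course can count as a feasibility success

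*Protocol*

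**What the plan says.** **Endpoint.** The synopsis defines feasibility as the "Proportion of study participants that complete radiotherapy with" at least 90% of the prescribed dose. Section 16.1 puts the hypothesis as "at least 90% of the recruited patients complete combined systemic and local treatment with at least 90% of scheduled radiation dose administered". Neither names a reference dose.

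**Regimen.** The synopsis lists only 4 x 5 Gy (CTV1) and 4 x 7 Gy (CTV2) as study therapy. Section 10.4 states "The dose will be prescribed as 95%-PTV-coverage" and gives the same doses, 20 Gy and 28 Gy in four fractions, but under the label "Recommended treatment regime". Section 10.3 wants all four fractions within two weeks of the start.

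**Substitution.** Section 10.1 says that in specific situations "lower doses of radiotherapy may be necessary for adherence of dose constraints or to avoid radiation-induced complications such as perforation". Its examples are spinal metastases involving the canal or compressing the cord, and "metastases with infiltration of hollow organs". It continues: "In these cases, moderately hypo-fractionated or even conventionally fractionated regimens should be used". The next sentence sets a floor for total dose, above the equivalent of 50 Gy in conventional fractionation.

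**Exclusion.** Section 6 excludes patients in whom departmental normal-tissue constraints cannot be met. No criterion there names infiltration of hollow organs or risk of perforation. Section 16.1 adds: "Drop-out may happen either due to exclusion".

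**The concern.** The trial asks whether one new four-fraction regimen can be delivered. An included patient for whom that regimen was judged unsafe and replaced is evidence against feasibility. As the endpoint is worded, the prescribed and scheduled dose for that patient is the substitute course, and completing it meets the criterion. The error runs in one direction: it raises the rate. Three sites applying the same text could also score the same patient differently.

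The threshold changes meaning as well. On four fractions, 90% leaves no room for a missed fraction. A course of five weeks or so can lose some and still pass.

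**Working it through.** **1. The plan's own sample size.** Section 16.1 gives p0 = 0.90, p1 = 0.70, two-sided 5%, power 80% and a one-sample score test. (Its text attaches the 70% to non-feasible cases; only a feasible proportion of 0.70 gives the stated result.)

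n = [(1.960 x √(0.9 x 0.1) + 0.842 x √(0.7 x 0.3)) / 0.20]² = 23.70, rounded up to 24.

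With 30% drop-out, 23.70/0.7 = 33.9, or 34. Both stated figures reproduce, and the point disputes neither.

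**2. Can a substitute patient be in the analysis?**
- Section 10.1 has two triggers: dose constraints, and avoiding complications such as perforation.
- Section 6 matches the first trigger. Patients excluded for it before treatment are drop-outs under Section 16.1 and do not enter the rate.
- The second trigger has no matching exclusion.
- Section 10.3 places the protocol MRI in patients already included, and Section 10.6 allows three weeks from inclusion to the start of radiotherapy. The need for a substitute can therefore appear after inclusion.

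**3. Effect per patient.** Scoring one patient as a success instead of not feasible moves the rate by 1/24 = 4.2 points, or 1/34 = 2.9 points. N = 24 is the evaluable number; 34 is the number included before drop-out.

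**4. When would the verdict change?** z = (x/n − 0.9)/√(0.09/n). The test first rejects 90% on the low side at 6 not feasible of 24 (18/24) and at 7 of 34 (27/34, p = 0.040). For k substitutes and 0 to 5 other failures, the verdict differs between the two ways of scoring in:

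| k | N = 24 | N = 34 |
|---|---|---|
| 1 | 1 of 6 | 0 of 6 |
| 2 | 2 of 6 | 1 of 6 |
| 3 | 3 of 6 | 2 of 6 |

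These are counts of scenarios, not probabilities.

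Example at N = 24 with 3 substitutes and 3 other failures:
- substitutes scored as successes: 21/24 = 87.5%, z = −0.41, p = 0.68
- substitutes scored as not feasible: 18/24 = 75.0%, z = −2.45, p = 0.014
- the same 3 excluded before treatment: 18/21 = 85.7%, p = 0.51

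The example sits exactly on the rejection boundary. With 2 other failures instead of 3, the not-feasible scoring gives 19/24, p = 0.077, and the verdict does not change.

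**5. Power under an assumed share.** Suppose true completion of the study regimen is 70%, and a further share of all patients counts as feasible only through a substitute course. Exact probability of rejecting 90% at n = 24:

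| Assumed share | Apparent rate | Probability |
|---|---|---|
| 0% | 70% | 77% |
| 5% | 75% | 58% |
| 10% | 80% | 34% |
| 15% | 85% | 14% |
| 20% | 90% | 2.8% |

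The shares are assumptions; the protocol gives none.

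**6. The threshold.** 0.9 x 20 = 18 Gy and 0.9 x 28 = 25.2 Gy. Three of four fractions is 15/20 = 21/28 = 75%, so all four are needed at the planned fraction size. For an assumed substitute of 26 x 2 Gy = 52 Gy, which exceeds the 50 Gy floor, 0.9 x 26 = 23.4, so 24 fractions (48 Gy) pass with two missed.

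**7. Section 10.1 against itself.** Equivalent dose in 2 Gy fractions is D(d + α/β)/(2 + α/β). With assumed α/β of 10, 3 and 1.5 Gy, 4 x 5 Gy gives 25.0, 32.0 and 37.1 Gy, and 4 x 7 Gy gives 39.7, 56.0 and 68.0 Gy. A floor above 50 Gy is therefore higher than the study dose to PTV1 at each of these values, although the passage introduces substitution as a lowering of dose. For PTV2 the answer depends on α/β.

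**The case against.** The best reply is that the documents already point to one denominator. The synopsis gives only 4 x 5 / 4 x 7 Gy as study therapy, in the same table as the endpoint. Section 10.4 is the dose specification and lists no other doses. Section 10.3 assumes four fractions in two weeks, which a conventional course cannot meet. Section 16.1 states the aim as feasibility of hypofractionated treatment. This stands as evidence of intent. It does not define the denominator, and it does not override a current instruction in Section 10.1 to treat some patients otherwise.

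It is also fair that the fault lies partly in Section 10.1, and that withdrawing such patients as drop-outs would be another way to handle them. A SAP could settle the scoring. But this protocol states the endpoint and itself creates the alternative regimens, so the gap is here. Doses and fractions are recorded (Section 11.3) and listed (Section 16.3), so a reader could recompute the rate; the primary rate would still include the substitutes.

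A reader might infer that the feasibility verdict is likely to be wrong. The documents do not support that: they give no number of substitutes, and a single one changes the verdict in at most 1 of the 6 scenarios above. Nor do they support reading the protocol as intending substitutes to be successes, or as counting every patient who fails a dose constraint.

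**Conclusion.** The point holds as an undefined denominator in the primary endpoint, combined with a substitution clause that contradicts other sections. The literal reading biases the feasibility rate upward by 4.2 points per treated substitute at N = 24 (2.9 at N = 34). This rests on such patients being included, treated and kept in the analysis, which the perforation trigger allows. Their number is unknown, so the verdict changes and power losses above are illustrations and not predictions. The sample size is unaffected. The point is worth correcting because it touches the primary endpoint and one definition removes it.

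**What to change.** **Synopsis and Section 16.1.** Add: *The dose component of feasibility is met if the patient receives at least 90% of the regimen in Section 10.4, that is at least 18 of 20 Gy to PTV1 and at least 25.2 of 28 Gy to PTV2, which requires all four fractions. Included patients treated with an alternative regimen under Section 10.1 count as not feasible and are also reported separately.* Leave the systemic-treatment component of the Section 16.1 hypothesis as it is.

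**Section 10.1.** Align it with Sections 6 and 10.3. Remove substitution for dose constraints, including the spinal-canal and cord example where that is a dose-constraint case. Remove or correct the 50 Gy-equivalent floor, which contradicts the stated purpose of lowering the dose.

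**Cost.** One definition and a short revision of one section. No new data are needed, since Section 11.3 already records fractions and doses applied, and N stays at 24 evaluable and 34 included. The downside is that the reported feasibility rate may be slightly less favourable.
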